6.1.3 Method of treatment assignment

Treatment will be assigned centrally via Interactive Response Technology (IRT). All eligible subjects will be randomly assigned to one of the two treatment groups (0,5mg/kg or placebo) in a 1:1 ratio at baseline. Details of the IRT procedure will be described in the IRT manual.

Randomization will be stratified according to presence or absence of background of atopy.

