9.2.4 Inferential statistical analyses

The primary efficacy analysis of the percent change from baseline to week 4 of the weekly average of the peaks pruritus NRS, will be an ANOVA including the Treatment group as factor, presence and absence of background of atopy and country as a cofactors.

In addition to the per-protocol analysis, several sensitivity analyses on ITT population will be conducted for the primary endpoint. For ITT, NRS will be set to missing after rescue medication is used.

- The primary imputation method for any missing data will be the LOCF (Last observation carried forward) approach.
- Multiple Imputation (MI) using the Missing At Random (MAR) assumption will also be used. The MI procedure of the SAS system will be used to generate five sets of data with missing values imputed from observed data. It is expected that the pattern of missing data will be monotonic, with slight deviations being corrected by the Markov Chain Monte Carlo (MCMC) method of the MI procedure. Linear regression will be employed to model the missing NRS score, with the following covariates included in the imputation model: treatment and non-missing data from earlier timepoints. The imputed datasets will be analyzed using the methodology described for percent change from baseline in NRS score. The results from the analysis of the multiple imputed datasets will be combined by the MIANALYZE procedure of the SAS system. The seed number to be used will be the protocol number (115828).

For secondary endpoints:

The percent change from baseline to any visits of the weekly average of the peak and of the average pruritus NRS, will be analyzed separately via an ANOVA including the Treatment group as factor, presence and absence of background of atopy and country as a cofactors. The absolute change will be analyzed via an ANCOVA, same factors as the percent change but with including baseline NRS as a covariate.

IGA, DPS and PAS will be analyzed at any visits by the CMH test stratified by background of atopy and by country with the ridit transformation and the row mean difference statistic (FREQ procedure from SAS).

Proportion of subjects achieving success (IGA=0[clear] or IGA=1[Almost clear] with two point improvement from baseline) will be analyzed at each evaluation visit using the Cochran-Mantel-Haenszel (CMH) test stratified by background of atopy and by country with the ridit transformation and the general association statistic (FREQ procedure from SAS).

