#### 5.7.1.3 Handling of Missing Data

**Use of rescue therapy:** For the purpose of efficacy analysis, subjects receiving any rescue therapies will be considered as treatment failures. All efficacy data, except Observed Case (OC), will be set to missing after rescue medication is used. In OC analysis, observed data after subject has received rescue treatment will be included.

**Diary data:** If a subject has less than 5 diary entries in a week, the weekly prorated average scores will be set to missing. Otherwise the method of computing weekly score when data are missing will be mean replacement approach. i.e. calculation of the overall weekly score a given week as 7 times average of non-missing average of that week.

The following methods will be used to impute the missing values:

**Continuous endpoints:** To impute the missing values for the primary and secondary endpoints, the following imputation approaches will be carried out to assess the robustness of study conclusions with choice of imputation method.

For sensitivity analyses, continuous endpoints will be analysed using analysis of covariance (ANCOVA) including terms of treatment group, country, presence or absence of background of atopy (the stratification factor for randomization to the treatments) and the corresponding baseline value.

1. **Last Observation Carried Forward (LOCF):** The primary imputation method for any missing data will be the LOCF approach. The last observed post-baseline value will be used to replace missing values for continuous variables. For questionnaire-based variables, LOCF will be applied to missing individual questions first, and the value of the total (or sub-scale) score will be derived based on the imputed individual questions.
2. **Observed Case (OC):** No data will be imputed. The observed values are used in analysis, including assessments post rescue medication.
3. **Multiple imputation (MI) method under assumption missing at random (MAR):**

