Multiple Imputation (MI) using the Missing At Random (MAR) assumption will also be used. The MI procedure of the SAS system will be used to generate five sets of data with missing values imputed from observed data. It is expected that the pattern of missing data will be monotonic, with slight deviations being corrected by the Markov Chain Monte Carlo (MCMC) method of the MI procedure. Linear regression will be employed to model the missing NRS score, with the following covariates included in the imputation model: treatment and non-missing data from earlier timepoints.

- **Analysis phase:** The imputed datasets will be analyzed using the methodology described for percent change from baseline in NRS score.
- **Pooling phase:** The results from the analysis of the multiple imputed datasets will be combined by the MIANALYZE procedure of the SAS system.

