### 5.7.2 Primary Efficacy Endpoint

Pruritus Numeric Rating Score (NRS) is a scale to be used by the subjects to report the intensity of their pruritus (itch) during the last 24 hours all along the study from the first screening visit to the follow up visit.

The primary variable for the assessment of efficacy is the percent change from baseline in NRS at week 4 of average of the peak pruritus.

An analysis of variance (ANOVA) model will be used to test the difference between the nemolizumab and placebo treatments with percent change from baseline in NRS scores at week 4 being the dependent variable, and treatment, presence or absence of atopy and country terms as factors.

A 95% Confidence for the difference in LSmeans of treatments and p-value will be calculated based on contrast test statistics.

Other covariates may be explored and will be added into the model, if appropriate.

**Sensitivity analysis:** The robustness of the primary analysis will be investigated by performing the sensitivity analyses, as described in 5.7.1.3.

**Subgroup analysis:** The homogeneity of the treatment effect for a number of important subgroups will be investigated, as described in 5.7.1.6.

A by-subject listing of the primary efficacy data will be provided. In addition, a boxplot and line plots showing the mean percent change and 95% CI from baseline in NRS over time within each treatment group will be produced for ITT and PP populations.

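### The multiple-imputation check on the primary endpoint uses only five imputations and, as a separate weakness, leaves atopy and country out of the imputation model; both are cheap to repair

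*SAP*

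**What the plan says.** SAP 5.7.1.3 makes LOCF the lead method: "The primary imputation method for any missing data will be the LOCF approach". Multiple imputation under missing at random is listed as a further approach. It is to "generate five sets of data with missing values imputed from observed data", with these "covariates included in the imputation model: treatment and non-missing data from earlier timepoints". Protocol 9.2.4 has the same specification and adds a seed: "The seed number to be used will be the protocol number (115828". The SAP does not repeat the seed.

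For the analysis step SAP 5.7.1.3 says: "The imputed datasets will be analyzed using the methodology described for percent change from baseline in NRS score". That model, in SAP 5.7.2, is an ANOVA with "treatment, presence or absence of atopy and country terms as factors". The same SAP section also prescribes a model for its sensitivity checks, under which "continuous endpoints will be analysed using analysis of covariance (ANCOVA) including terms of treatment group, country, presence or absence of background of atopy", together with the baseline value. Whichever of the two is applied to the imputed data, atopy and country are in it.

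Protocol 6.1.3 states: "Randomization will be stratified according to presence or absence of background of atopy". Protocol 3.2 gives the reason: atopy background is regarded as prognostic.

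**The concern.** There are two faults, and they need to be kept apart.

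**Number of imputations.** A pooled estimate from a finite number of imputations carries simulation noise on top of sampling error. With five, that noise may be large enough to matter when the result is close to the 5% level. Fixing the seed makes the number repeatable, but it does not bring it closer to the value that many imputations would give.

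**Imputation model.** Values are imputed as though atopy and country told us nothing beyond treatment and earlier scores, and are then analysed in a model that adjusts for both. If either factor predicts the Week 4 score or its absence, the pooled difference and its standard error can move.

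What is at stake is the value of one robustness check. For the continuous primary endpoint the SAP plans LOCF, observed cases and this multiple imputation; the missing-not-at-random imputation in SAP 5.7.1.3 is listed only for binary endpoints. So this is the only model-based imputation against which LOCF will be compared.

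**Working it through.** **Inputs from the documents.** SD 35, true difference 30 points, two-sided 5%, 90% power, 30 evaluable and 35 randomized per group (SAP 5.10); 5 imputations (SAP 5.7.1.3); Week 4 diary window Days 22–28 (SAP 5.2); rescue permitted from Day 29 (SAP 5.5.3.3).

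**The plan's own figure.** With effect size 30/35 = 0.857, the noncentral t distribution gives 89.4% power at 29 per group and 90.4% at 30. The stated 30 is reproduced. Going from 30 to 35 allows a loss of 5/35 = 14.3%, which covers major deviations as well as dropouts.

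**Assumption.** No missing-data rate is stated. I take 10–30% missing information as a range. Permitted rescue starts after the Week 4 window, so missing Week 4 scores should come mainly from dropout or from weeks with fewer than five diary entries. The upper end is therefore generous.

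**Monte Carlo error.** The complete-data standard error is 35 × √(2/35) = 8.37 points. The Monte Carlo SD of the pooled estimate, as a share of its standard error, is about √(FMI/m), where FMI is the fraction of missing information and m the number of imputations.

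| FMI | m = 5 | m = 50 | m = 100 |
|---|---|---|---|
| 10% | 0.141 (1.2 points) | 0.045 (0.37) | 0.032 (0.26) |
| 14.3% | 0.169 (1.4) | 0.053 (0.45) | 0.038 (0.32) |
| 30% | 0.245 (2.1) | 0.077 (0.65) | 0.055 (0.46) |

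**Effect on a borderline p-value.** p = 0.040 corresponds to z = 2.05. Moving one Monte Carlo SD at m = 5 gives z = 2.05 ± 0.141, or p = 0.028–0.056, at 10%. At 30% it gives z = 2.05 ± 0.245, or p = 0.022–0.071.

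**Effect at the design difference.** z = 30/8.37 = 3.59. Losing two Monte Carlo SDs at 30% leaves 3.59 − 0.49 = 3.10, p about 0.002.

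**Simulation.** I used 35 per arm, SD 35, missing-at-random dropout, regression imputation, ANOVA on treatment, atopy and four countries, Rubin's rules, and 500 seeds on a fixed borderline dataset. Assumptions outside the documents are a correlation between successive weekly scores of 0.6 or 0.8, missing fractions of 7%, 14.3% and 25%, and modest atopy and country effects. With 14.3% missing, correlation 0.6 and the SAP imputation model:

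| m | central 95% of p over seeds | seeds with p < 0.05 |
|---|---|---|
| 5 | 0.015–0.100 | 70% |
| 20 | 0.026–0.057 | 88% |
| 50 | 0.030–0.050 | 98% |
| 100 | 0.032–0.047 | 99% |

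At m = 5 the range is 0.024–0.068 with 7% missing and 0.014–0.140 with 25% missing (both at correlation 0.6). A correlation of 0.8 narrows these to 0.026–0.064 and 0.022–0.079.

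**Omitted covariates, tested separately.** Adding atopy and country at m = 5 left the seed spread unchanged: Monte Carlo SD over standard error 0.159 against 0.156, p range 0.015–0.094 against 0.015–0.100 (14.3% missing, correlation 0.6). It can move the answer itself. At m = 100 with 25% missing, the median p went from 0.042 to 0.082 (correlation 0.6) and from 0.040 to 0.055 (0.8). At 14.3% missing the shifts were small: 0.039 to 0.039 and 0.040 to 0.037. Each figure comes from a single simulated dataset, so they show that the choice can matter, not how large or in which direction the effect would be here.

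**The case against.** The strongest case on the other side is that little depends on this analysis. Multiple imputation sits behind LOCF, no decision rule is tied to its p-value, and the observed-case and per-protocol analyses are also planned and carry no simulation noise. At the assumed effect, p is far from 0.05. All of this stands, and it limits the point to an inexpensive improvement.

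Three stronger readings are tempting, and the documents do not support them.

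- *That the seed could be chosen to suit the result.* Protocol 9.2.4 fixes it in advance at 115828. What remains is the noise in that single pre-specified draw, and a gap in the SAP, which does not carry the seed over.
- *That the missing covariates cause the dependence on the draw.* They do not: the spread is the same with or without them. It comes from the number of imputations and the amount of missing information.
- *That the trial's conclusion is likely to flip.* In simulations at the design effect with 14.3% missing (correlation 0.6), the typical p was about 0.001. In 18.5% of simulated trials (36% at 25% missing) the 40 seeds tried did not all fall on the same side of 0.05, but the trial will use one draw, not 40.

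It is also fair to say that earlier timepoints arguably already include baseline NRS, so naming it only clarifies the plan. The choice between 50 and 100 imputations is largely preference.

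**Conclusion.** The point holds in two separate parts, both minor.

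1. Five imputations leave Monte Carlo error of about 14–25% of the standard error if missing information is 10–30%. A borderline result, p about 0.04, could be reported on either side of 0.05 by the chance of the draw. At the design effect the conclusion would usually not change. The missing-information range and the simulated correlations are assumptions; the nearest figure in the documents is the 14.3% allowance, which also covers major deviations.
2. The imputation model omits atopy, the randomization stratum that the protocol calls prognostic, and country, although the analysis model contains both. This can shift the estimate and its standard error, and a larger number of imputations does not cure it. Its size in this trial cannot be derived from the documents.

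The primary LOCF analysis is unaffected.

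**What to change.** In SAP 5.7.1.3:

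- Use at least 50, preferably 100, imputations. At 100 the Monte Carlo SD falls to 0.26–0.46 points over the same range.
- Add atopy and country to the imputation model, coded as in the analysis model, and name baseline NRS explicitly alongside the earlier weekly means.
- Restate seed 115828 from protocol 9.2.4, and report the Monte Carlo error with the pooled result.

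The cost is one changed parameter, two added covariates and a few words of text. Computing time is negligible, no new data are needed, and the primary analysis stays as it is.

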**Binary endpoints:**

All missing values will be treated as a Non-Responder for the binary endpoints. If a subject withdraws from the study, all assessments after withdrawal will be considered as Non-Responder.

- LOCF, OC, MI under missing not at random assumption approaches will be used as sensitivity analysis to impute the missing values for the selected secondary endpoints as appropriate. For sensitivity analyses, binary endpoints will be analysed using a Cochran-Mantel-Haenszel (CMH) test stratified by, presence or absence of background of atopy and country (Australia, France, Germany, Poland, and US)

There will be no imputation for missing laboratory and vital sign data.

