PP and ITT (Criteria will be set to missing after rescue medication is used and imputed to LOCF, for continuous outcomes and to failure for binary outcomes) will be conducted on secondary endpoints.

DLQI data will be analyzed on observed cases by CMH test test stratified by background of atopy and by country with the ridit transformation and the row mean difference statistic (FREQ procedure from SAS) on the data in categories and also in terms change from baseline via an

ANCOVA including treatment, baseline DLQI as a covariate, background of atopy and country as cofactors

The absolute and the percent change in weekly average sleep disturbance NRS from baseline up to week 4 will be analyzed by CMH test stratified by background of atopy and by country with the ridit transformation and the row mean difference statistic (FREQ procedure from SAS)

The PD parameters will be visualized by boxplots (with a logarithm base 10 Y axis where needed). The compound effect will be estimated by Student's t test comparing the change at D85 from D1 for CD14152 vs the change at D85 from D1 for placebo (or other if more appropriate). The multiple testing problem will be taken into account by the Benjamini-Hochberg approach (1995)(or other if more appropriate).

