#### 4.2.1.7 Dermatology Life Quality Index (DLQI)

DLQI is a validated 10-item questionnaire, covering domains including symptoms/feelings, daily activities, leisure, work/school, personal relationships and treatment. Subject will rate each question ranging from 0 (not at all) to 3 (very much), and the total score ranges from 0 to 30, with a higher score indicating a poorer quality of life. Please note that "Not relevant" is scored as 0, and Question 7 'Yes – prevented working or studying' is scored as 3. DLQI will be given only to the subset of subjects who fluently speak a language in which the questionnaire is presented (based on availability of validated translations in participating countries). This assessment will be performed by the subject on the provided electronic device at baseline, Week 4, and Week 12, and in case of Early termination visit / Unscheduled visit, if applicable.

For general inflammatory skin conditions, a change in DLQI score of at least 4 points is considered clinically important. Refer to Appendix 3 for details on scoring, data handling rules, and analysis on DLQI.

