**Intent-to-Treat Population (ITT):**

The ITT population will consist of all randomized subjects.

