#### **5.7.4 Other Efficacy Endpoints**

##### **Dermatology Life Quality Index (DLQI)**

DLQI will be assessed at baseline, weeks 4, 12, or early termination visit when applicable.

The DLQI score will be categorized as follows:

- 0-1 = no effect at all on subject's life
- 2-5 = small effect on subject's life
- 6-10 = moderate effect on subject's life
- 11-20 = very large effect on subject's life
- 21-30 = extremely large effect on subject's life

The DLQI can be analyzed under 6 sub-scales, namely, symptoms and feelings (question 1 and 2), daily activities (question 3 and 4), leisure (question 5 and 6), work and school (question 7), personal relationships (question 8 and 9), and treatment (question 10). For general inflammatory skin conditions, a change in DLQI score of at least 4 points is considered clinically important.

The primary study population for all QoL and productivity data will be the ITT Population. DLQI will be summarized by treatment group and visit. By-subject listings of these data should be provided.

Change from baseline in DLQI at each visit will be analyzed using ANCOVA with treatment group, baseline DLQI as a covariate, background of atopy and country as cofactors. In addition, the following analyses will be performed:

- A shift table (by visit) will be generated using the categories described above. Change from baseline in each sub-scale at each visit will be analyzed as the efficacy endpoint using ANCOVA.
- Proportion of subjects achieving a change in DLQI score of at least 4 points at each Visit up to week 12 will be analyzed using a CMH test with ridit scores between nemolizumab and placebo, stratified by background of atopy (presence or absence) and country.

Number and percentage of subjects will also be provided for the following DLQI score categories at each visit for the above categories and analyze using CMH test stratified by background of atopy and by country with the ridit scores.

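### If any randomized subject is not given the DLQI for language reasons, the SAP's missing-equals-non-responder rule counts that subject as a DLQI failure in the 4-point responder analysis

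*SAP*

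**What the plan says.** Four statements in the SAP combine.

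- Section 4.2.1.7, on who receives the questionnaire: "DLQI will be given only to the subset of subjects who fluently speak a language in which the questionnaire is presented". Protocol 7.1.1.5 has the same restriction. The inclusion criteria in protocol 5.3 do not require fluency in such a language.
- Section 5.7.4, on the analysis: "Proportion of subjects achieving a change in DLQI score of at least 4 points at each Visit up to week 12 will be analyzed", by a CMH test stratified by atopy background and country.
- Section 5.7.4, on the population: "The primary study population for all QoL and productivity data will be the ITT Population". Section 5.4 defines it: "The ITT population will consist of all randomized subjects".
- Section 5.7.1.3, on missing data: "All missing values will be treated as a Non-Responder for the binary endpoints".

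No exemption is written for subjects who were never to be given the questionnaire. SAP Appendix 3 deals with unanswered or wrongly completed items, not with a form that was never handed over. The alternative methods for binary endpoints (LOCF, observed case, multiple imputation) "will be used as sensitivity analysis to impute the missing values for the selected secondary endpoints as appropriate", whereas SAP 4.2.2.3 places the DLQI among the other efficacy endpoints.

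**The concern.** Non-responder imputation is a reasonable convention when a value is missing because the subject dropped out or took rescue, since the gap may reflect a poor outcome. A DLQI that is absent because no suitable language version exists says nothing about outcome. It is fixed before the first injection and is the same at baseline and at every later visit.

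Followed literally, the rule adds certain failures to both arms. The reported responder rates fall, the crude difference is pulled toward zero, and a chance imbalance in these subjects moves the comparison in either direction. The SAP also becomes uneven within one instrument. A subject with no DLQI has neither the baseline covariate nor an outcome for the ANCOVA of change and drops out of it, yet stays in the responder analysis as a failure.

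**Working it through.** **The plan's own figure.** The only sizing figure is for the primary endpoint: difference 30, SD 35, two-sided 5%, 90% power, at least 30 per group (protocol 9.3, SAP 5.10). A two-sample t test gives 29.6, rounded up to 30, so it reproduces. Neither document states a DLQI responder rate, a DLQI power or the number of subjects not given the DLQI.

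**Inputs.** From the documents: 35 randomized per arm, 1:1 allocation, two-sided 5%. Assumed for illustration: true responder rates of 70% (nemolizumab) and 40% (placebo) among assessable subjects, and q = 5%, 10% or 20% not given the DLQI in each arm.

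**Difference.** Under the rule each arm's rate is p(1-q), so the difference is (1-q)(pT - pC):

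- q = 5%: 66.5% - 38.0% = 28.5 points
- q = 10%: 63.0% - 36.0% = 27.0 points
- q = 20%: 56.0% - 32.0% = 24.0 points

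**Power, ignoring strata.** Power = Φ(d/SE - 1.96), with SE = √{[pT(1-pT) + pC(1-pC)]/n}. The rule as written uses the diluted rates with n = 35. Leaving these subjects out uses 70% v 40% with n = 35(1-q).

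| q | Rule as written | Left out | Loss |
|---|---|---|---|
| 0 | 75% | 75% | 0 |
| 5% | 70% | 73% | 3 points |
| 10% | 65% | 71% | 6 points |
| 20% | 55% | 66% | 11 points |

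For q = 20%: 0.24/0.1151 - 1.96 = 0.12, giving 55%; and 0.30/0.1268 - 1.96 = 0.41, giving 66%. Using the pooled variance under the null instead gives 52.6% v 62.2% at q = 20%, a loss of similar size.

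**Chance imbalance.** Suppose 14 of 70 subjects are not given the DLQI. A 7/7 split gives 24.0 points. A split of 9 nemolizumab and 5 placebo gives 0.70 × 26/35 - 0.40 × 30/35 = 17.7 points. The reverse split gives 0.70 × 30/35 - 0.40 × 26/35 = 30.3 points. The factor (1-q) therefore holds in expectation, not in every sample.

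**Effect of stratification.** Take 28 assessable subjects per arm in two equal strata, with responders 10/14 v 6/14 and 10/14 v 5/14. The CMH chi-square is 5.65. Adding 7 failures per arm as a separate stratum leaves it at 5.65, because a stratum with no responders contributes nothing. Spreading them over the two strata (17 and 18 per arm) lowers it to 4.57. The crude difference falls from 20/28 - 11/28 = 32.1 points to 20/35 - 11/35 = 25.7 points in both cases.

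**The case against.** The strongest objection is that no affected subject is shown to exist. The restriction depends on which translations are available, and neither document names a country or language without one. This stands: q may be zero, and every size above is conditional.

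Three stronger readings are tempting, and the documents do not support them.

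- A reader might infer that the quality-of-life evaluation as a whole is compromised. It is not. The 4-point proportion is absent from the endpoint list in SAP 4.2.2.3 and appears only among the additional analyses in 5.7.4. The binary rule does not enter the ANCOVA of DLQI change.
- A reader might infer that the SAP overturned a protocol rule for this endpoint. Protocol 9.2.4 does say "DLQI data will be analyzed on observed cases by CMH test", but this covers a test on score categories and an ANCOVA of change. The supplied protocol has no 4-point DLQI responder. The SAP is also written to protocol Amendment Version 2.0, which is not among the documents reviewed.
- A reader might infer that power must fall. As shown, the stratified CMH statistic is unchanged if these subjects fill whole country-by-atopy strata, which is possible because language may follow country. The crude difference still shrinks.

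Two textual defences are weaker. SAP 5.2 uses subjects providing data as the denominator, but for descriptive tables. The limitation to selected secondary endpoints in 5.7.1.3 applies to the sensitivity methods, not to the main rule. Neither creates an exemption, although together they leave room for two programmers to produce different rates.

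**Conclusion.** The point holds conditionally. If any randomized subject is not given the DLQI for language reasons, the SAP as written scores that subject as a failure at each DLQI visit in the 4-point analysis. With equal shares per arm, the expected crude difference is multiplied by (1-q). The losses of 1.5, 3 and 6 percentage points in the difference, and of about 3, 6 and 11 points in power, rest on assumed rates of 70% v 40%, assumed values of q, and an unstratified test.

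With balanced shares the bias is toward no difference; with unbalanced shares it can go either way. The primary analysis and the sample size are untouched. This is a modest defect in an additional analysis, worth settling before unblinding because the correction is so small.

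**What to change.** In SAP 5.7.1.3 and 5.7.4, state that the DLQI responder proportion is computed among randomized subjects who were eligible to be given the DLQI at baseline, using a flag fixed before treatment. Within that set, keep non-responder imputation for later missing values and for rescue. Report by arm the number of subjects not given the DLQI.

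The flag should record eligibility for the questionnaire, not possession of a scored baseline. Requiring a scored baseline would also remove subjects who were given the form but missed it or left two or more items blank, which is broader than the defect.

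The cost is one SAP sentence and a denominator flag. The small downside is an analysis set slightly smaller than all randomized. Because membership does not depend on treatment, the randomized comparison is preserved within it. If every subject was given the DLQI, the change has no effect.
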